5.2 Protocol Deviations

Major protocol deviations are compliance issues that impact subject safety or the scientific integrity of the study data. All deviations will be evaluated and classified as major or minor by the study team before database lock and unblinding. Major and minor deviations will be summarized by treatment group with counts and percentages of subjects with at least 1 deviation. If a subject has both minor and major deviations, that subject will be counted as having a major deviation. All deviations will be listed.

5.3 Disposition of Subjects

The following subject data will be summarized for each treatment group and overall for the ITT and mITT populations:

- Overall number of subjects screened
- Number of subjects randomized
- Number of subjects randomized but not treated
- Number and percentage of subjects in each analysis population
- Number and percentage of subjects who completed the study
- Number and percentage of subjects who prematurely discontinued the study as well as number and percentage of subjects for each reason for discontinuation.

Percentages will be calculated using the ITT or mITT population as a denominator. All disposition data will be listed.

An additional summary of subjects enrolled by region and site for each treatment group and overall will be presented. A listing of subject enrollment and disposition information will be provided for all subjects. An additional listing of subjects who prematurely discontinued the study will also be presented. Inclusion of subjects into each of the analysis populations (ITT, Safety, mITT, and PK) will also be listed.

6 DEMOGRAPHICS AND BASELINE CHARACTERISTICS

6.1 Demographics and Baseline characteristics

Descriptive statistics of the general demographic and Baseline characteristics for each treatment group and overall will be presented. Baseline variables age (years), height (cm), weight (kg), body mass index (BMI, kg/m²), both baseline HAI titers (H1 and H3), and time since onset of influenza symptoms will be summarized with n, mean, SD, median, minimum and maximum; time to onset of influenza will also be dichotomized (< 48 hours or ≥ 48 hours) and summarized with counts and percentages. Counts and percentages will be presented for each category of gender, race, ethnicity, vaccination status, confirmed influenza A by method of diagnosis (RAT, PCR, TCID₅₀), and influenza subtype.

The demographic and Baseline data will be summarized in the ITT and mITT populations. All demography and Baseline data will be listed.

The following definitions and conversions will be used:

- Height (in) *2.54 = height (cm)
- Weight (lb) /2.2 = weight (kg)
- BMI = weight (kg)/ height² (m²)
- Time since onset of influenza (hours) = date/time of infusion start – date/time of onset of symptoms. If onset time is missing, it will be imputed as 00:00 on the 24-hour clock.

6.2 Medical history

Medical history will be coded using the Medical Dictionary for Regulatory Activities (MedDRA) Version 19.1 and summarized by System Organ Class (SOC), Preferred Term (PT), and treatment with counts and percentages in the ITT and mITT populations. A subject will only be counted once in an SOC and an SOC/PT combination. All medical history data will be listed.

6.3 Prior medications

Prior medications are defined as medications that start on or before the date of study drug IV infusion and/or are declared as “Pre-study” on the medications eCRF page. Protocol-specified pre-treatment medications will be summarized as prior medications. Prior Medications will be coded with the World Health Organization Drug (WHODrug) Dictionary, Sep 2016 and summarized by Anatomical Therapeutic Chemical (ATC) Level 4, PT, and treatment in the ITT and mITT populations. A subject will only be counted once in an ATC class and an ATC class/PT combination. All eCRF medication data will be listed, including the WHO Drug ATC class, PT and the investigators verbatim description of the medication.

7 CONCOMITANT MEDICATION

Concomitant medications are defined medications that are being taken while on study drug. Any prior medication that cannot be confirmed as stopping before the start of study drug IV infusion will be classified as both a prior and a concomitant medication. Concomitant medications will be coded with the WHODrug, Sep 2016 dictionary, and summarized by ATC Level 4, PT, and treatment in the safety population. A subject will only be counted once in an ATC class and an ATC class/PT combination. Medications that are ongoing on the date of study drug IV infusion will be summarized as both prior and concomitant. All eCRF medication data will be listed, including the WHO Drug ATC class, PT term, the investigators verbatim description and classification as Prior, Concomitant or Both.

A separate listing of concomitant antiviral medications taken for influenza through study day 100 will also be presented. Antiviral medications will be defined as those medications that exclude a subject from the sensitivity analysis of the overall FluPRO and viral shedding analyses.

8 TREATMENT EXPOSURE AND COMPLIANCE

The duration of infusion in minutes and volume of infusion will be summarized by treatment group with n, mean, SD, median, minimum and maximum in the Safety and mITT populations. The number and percentage of subjects in each treatment group who received diphenhydramine per protocol, received an NSAID per protocol, had an infusion interruption of > 15 minutes, and did not receive the full infusion will also be summarized in the Safety and mITT populations. If there are a large number of interruptions (10% or more), incomplete infusions, or subjects not receiving the protocol-specified pre-treatment medications, the duration of infusion and volume of infusion summaries may be repeated with subsets based on these dosing parameters. The decision to generate any subset summaries will be made before unblinding the study.

9 EFFICACY ANALYSES

The primary objective of this study is the safety and tolerability of a single IV dose of VIS410. Safety analyses are described in Section 13.

9.1 Main Efficacy Analysis

9.1.1 Patient Diary - Influenza Patient Reported Outcomes (FluPRO)

The FluPRO is a 32 question instrument that assesses occurrence and severity of influenza symptoms over the last 24 hours. The instrument questions, and the conversion from text to numeric values, are presented in Sec. 17.3.

The FluPRO data is collected at Day 1: Baseline, then every day through Day 10. These data will be summarized at each visit with counts and percentages by treatment group, including a combined low-dose and high-dose VIS410 group. This analysis will be performed using the mITT population.

The domain, component, and total symptom scores for an individual will be calculated as the mean of the questions that are non-missing. The minimum data requirement for calculating each of the domain symptom scores is: nose 3 of 4 items, throat 2 of 3 items, eyes 2 of 3 items, chest/respiratory 5 of 7 items, gastrointestinal 3 of 4 items, and body/systemic 8 of 11 items. Total symptom scores will only be calculated if the conditions of missing data for all domains are met.

The domain symptom scores are defined as:

- Nose: Running or dripping nose, congested or stuffy nose, sneezing, sinus pressure
- Throat: Scratchy or itchy throat, sore or painful throat, difficulty swallowing
- Eyes: Teary or watery eyes, sore or pain eyes, eyes sensitive to light
- Chest/Respiratory: Trouble breathing, chest congestion, chest tightness, dry or hacking cough, wet or loose cough, coughing, coughed up mucus or phlegm
- Gastrointestinal: Nausea, stomach ache, vomiting, diarrhea
- Body/Systemic: Felt dizzy, head congestion, headache, lack of appetite, sleeping more than usual, body aches or pains, weak or tired, chills or shivering, felt cold, felt hot, sweating

The component symptom scores are defined as:

- Upper Respiratory Tract: Runny or dripping nose, congested or stuffy nose, scratchy or itchy throat, sore or painful throat, sneezing, difficulty swallowing, teary or watery eyes, sore or painful eyes, eyes sensitive to light,
- Lower Respiratory Tract: Trouble breathing, chest congestion, chest tightness, coughing, dry or hacking cough, wet or loose cough, coughed up mucus or phlegm
- Generalized: Nausea, vomiting, diarrhea, stomach ache, felt dizzy, sinus pressure, head congestion, headache, lack of appetite, sleeping more than usual, body aches or pains, weak or tired, chills or shivering, felt cold, felt hot, sweating

Time to resolution (in days) for the total symptom score, each domain symptom score (nose, throat, eyes, chest/respiratory, gastrointestinal, body/systemic) and each component symptom score (upper respiratory tract, lower respiratory tract, and generalized) will be summarized using n, mean, SD, median, minimum, and maximum. Kaplan-Meier methods will also be used to calculate the median time, 25th percentile, and 75th percentile time to resolution. These summaries will be by treatment group and include the combined low-dose and high-dose VIS410 groups in the mITT population. For individual symptom questions 1 to 32, a value of 0 or 1 corresponds to resolution of that symptom. Time to resolution of the total symptom, domain symptom scores and component symptom scores will be defined as the maximum time to resolution for the individual questions that comprise that total, domain or component symptom score.

The duration of an individual symptom will be defined as the earliest visit day from 2 consecutive answers of ‘no symptom’ defined as ‘Not at all’ or ‘A little bit’ for questions 1 – 27; ‘Never’ or ‘Rarely’ for questions 28 - 30 and ‘0 times’ or ‘1 time’ for questions 31 and 32. The duration of total symptom score, domain symptom scores, or component symptom scores will be primarily defined as the earliest visit day from 2 consecutive means ≤ 1.0 ; and as an exploratory endpoint as the maximum value of duration across the individual symptoms questions that comprise that total, domain or component symptom score. A missing value cannot contribute to the 2 consecutive ‘no symptom’ days. If a subject has ‘no symptoms’ at Baseline for a question, total symptom score, domain symptom scores, and component symptom scores, duration will be defined as zero for that question. If a subject has not had 2 consecutive ‘no symptom’ responses or 2 consecutive means ≤ 1.0 by the Day 10 FluPRO survey, the subject’s data will be listed as “>10” and summarized as 10 days. Kaplan-Meier methods will also be used to calculate the median time, 25th percentile, and 75th percentile time to resolution.

The total symptom score, the 6 domain symptom scores, and the 3 component symptom scores will be summarized by treatment group at each visit (including change from baseline and percent change from Baseline to each visit), including the combined low-dose and high-dose VIS410 group with n, mean, SD, median, minimum, and maximum by treatment group, including a combined low-dose and high-dose VIS410 group.

The count and percentage of subjects with a mean score ≤ 1.0 for the total symptom score, 6 domain symptom scores, and 3 component score will be summarized at each post-baseline visit. An additional summary of counts and percentages of subjects with a score of 0 or 1 for all of the individual symptom scores composing the total symptom score, 6 domain symptom scores, and 3 component symptom scores will also be presented for each post-baseline visit. These summaries will also be presented by region: USA, South Africa, and the rest of the world.

Area under the curve (AUC) for the total symptom score, 6 domain symptom scores, and 3 component symptom scores will be calculated using the linear trapezoidal rule, i.e. $AUC_{t_i, t_{i+1}} = 1/2 * (S_i + S_{i+1}) * (t_{i+1} - t_i)$ where S_i is the total symptom score at time point t_i . All time points from pre-dose to Day 10 will be considered.

A sensitivity analysis of the total symptom score, domain symptom scores, and component symptom scores will be conducted by repeating the above analysis in the mITT population,

excluding subjects who received antiviral therapy for influenza during the first 10 days of the study. Determination of applicable antiviral therapy for influenza will be defined before the study is unblinded.

Additional exploratory analysis, including but not limited to evaluation of sums instead of means of symptom scores, may be performed for the total symptom score, 6 domain symptom scores, and 3 component symptom scores.

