2.2 SECONDARY OBJECTIVES

- Evaluate the efficacy of VIS410 compared with placebo on the time to alleviation of clinical symptoms of acute uncomplicated influenza
- Evaluate the effect of VIS410 on severity of influenza infection
- Assess the pharmacokinetics of VIS410 in serum
- Assess the effects of VIS410 on viral shedding
- Assess the immunogenicity of VIS410

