9.3 STATISTICAL ANALYSIS

VIS410 endpoints will compare aggregated VIS410 data as well as different dose levels of VIS410 to the placebo arm. Further details of the statistical methodology will be described in the statistical analysis plan (SAP).

9.3.1 *Analysis Populations*

The following analysis populations will be defined for the study:

Intent-to-Treat (ITT): All subjects randomized to treatment.

Modified Intent-to-Treat (mITT): All subjects who receive IV study drug and are confirmed influenza A positive by a molecular test at the central virological laboratory.

Safety Population: All ITT subjects who received IV study drug.

PK Population (PK): All subjects who received IV study drug with at least 1 PK parameter that can be calculated.

9.3.2 *Initial Characteristics of the Subject Sample*

Summary statistics will be provided per treatment group for demographic (e.g., age, height, weight, Body Mass Index, race, gender) and other initial subject characteristics (physical examination, medical history, concomitant diseases) will be provided per treatment group and for the total group. The ITT population will be used for the summaries.

Prior and concomitant medications will be coded using the World Health Organization Drug Dictionary.

9.3.3 *Pharmacokinetics*

Standard non-compartmental approaches using Phoenix WinNonlin (Pharsight Corporation, Princeton, NJ, USA; Version 6.3 or higher) will be used to estimate the PK parameters in serum and nasopharyngeal secretions (see Section 7.2.3) described below. All calculations will use the actual times recorded in the EDC system for dosing and sampling. Individual and mean (\pm SD) or median concentrations versus time profiles will be plotted by study period on both linear and logarithmic scales. Additional plots and PK parameters may be generated as appropriate. The PK population will be used for the summaries.

Serum Pharmacokinetics

Serum concentrations and the computed PK parameters will be listed by subjects for VIS410. Summary statistics of serum concentrations and PK parameters will be presented including means, geometric means, standard deviations, CV, medians and ranges, as appropriate.

Additional analyses and summaries may be generated as appropriate.

The following PK parameters will be determined for VIS410 in serum:

- C_{\max} : maximum observed serum concentration
- T_{\max} : time of C_{\max}

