- $AUC_{0-\infty}$: area under the serum concentration-time curve from time 0 extrapolated to infinity
- $AUC_{0-\text{last}}$: area under the serum concentration-time curve from time 0 to the last measurable concentration
- $t_{1/2}$: terminal elimination half-life
- CL: total clearance
- V_d : volume of distribution

PK data from this study will be also analyzed by population PK modeling.

Nasopharyngeal Secretion Pharmacokinetics

Nasopharyngeal secretion concentrations and the computed PK parameters will be listed by subject for VIS410. Summary statistics of nasopharyngeal secretion concentrations and PK parameters will be presented including means, geometric means, standard deviations, CV, medians and ranges, as appropriate. Additional analyses and summaries may be generated as appropriate.

The following PK parameters will be determined for VIS410 from nasopharyngeal secretions:

- C_{\max} : maximum concentration observed from nasopharyngeal secretions
- T_{\max} : time of C_{\max}
- $AUC_{0-\infty}$: area under the nasopharyngeal secretion concentration-time curve from time 0 extrapolated to infinity
- $AUC_{0-\text{last}}$: area under the nasopharyngeal secretion concentration-time curve from time 0 to the last measurable concentration
- $t_{1/2}$: terminal elimination half-life
- Ratio of nasal:serum AUC

Additional PK parameters may be determined as appropriate.

9.3.4 *Viral Shedding*

Additional sensitivity analysis may be conducted excluding subjects that received concomitant antiviral therapy during the course of the study.

- One-way analysis of variance (ANOVA) (with treatment group as the factor) or other appropriate statistics detailed in the SAP to assess the difference between VIS410 treatment groups vs placebo in the area under the viral load-time curve (AUC) for influenza virus based on quantification of viral load from nasal swabs

- Descriptive statistics of the area under the viral load-time curve (AUC) for influenza virus based on quantification of viral load from nasopharyngeal swabs by treatment group.
- Descriptive statistics of the time to resolution of viral load and of the peak viral load by treatment group.

The mITT population will be used for the summaries.

9.3.5 *Signs and Symptoms of Influenza*

The difference between VIS410 and placebo will be assessed as outlined below.

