- Frequency tabulation of the occurrence and severity of each of the subject-reported symptoms of influenza-like illness by assessment time point and by treatment group
- Descriptive statistics of the duration of each of the subject-reported symptoms of influenza-like illness by treatment group

Additional sensitivity analysis may be conducted excluding subjects that received concomitant antiviral therapy during the course of the study. The mITT population will be used for the summaries. Additional populations may be analyzed as described in the SAP.

9.3.6 *Immunology*

Immunological assessments will be summarized by parameter, treatment group, and time point using descriptive statistics:

- Anti-VIS410 antibody titers by ADA in serum
- Anti-influenza A antibodies by HAI in serum
- HAI levels to determine a proper immune response to the influenza infection

The mITT population will be used for the summaries. Additional populations may be analyzed as described in the SAP.

Anti-Drug Antibodies

Anti-VIS410 antibody titer will be summarized by treatment group and by time point using descriptive statistics.

9.3.7 *Exploratory Pharmacokinetic/Pharmacodynamic Analyses*

Various techniques will be used to explore exposure-response relationships, and to compare the strength of the relationship between each independent variable (e.g., AUC, C_{max} , and concentration at specific time point) and the dependent variables (e.g., viral AUC, peak viral load, and time to cessation of viral shedding, clinical symptoms, and additional endpoints). These techniques may include graphical and statistical methods, including the creation of boxplots, spaghetti plots, histograms, and a variety of linear, nonlinear, or logistic regression techniques and time-to-event methods. If appropriate, continuous independent variables will be evaluated as such, and as categorical variables (grouping subjects into exposure categories).

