2.1.2 Secondary Objectives

- Evaluate the efficacy of 2 dose levels of VIS410 compared with placebo on the time to alleviation of clinical symptoms of acute uncomplicated influenza
- Evaluate the effect of 2 dose levels of VIS410 on severity of influenza infection
- Assess the pharmacokinetics of 2 dose levels of VIS410 in serum
- Assess the effects of 2 dose levels of VIS410 on viral shedding
- Assess the immunogenicity of 2 dose levels of VIS410

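### Time to symptom alleviation is meant to be compared with placebo, but the SAP prespecifies only per-arm descriptive statistics for it, with no between-arm difference and no confidence interval

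*SAP*

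**What the plan says.** The objective is comparative in both documents. Protocol 2.2 reads "Evaluate the efficacy of VIS410 compared with placebo on the time to alleviation of clinical symptoms of acute uncomplicated influenza". SAP 2.1.2 makes it specific to dose: "Evaluate the efficacy of 2 dose levels of VIS410 compared with placebo on the time to alleviation of clinical symptoms of acute uncomplicated influenza". Protocol 9.3 states the intended contrasts: "VIS410 endpoints will compare aggregated VIS410 data as well as different dose levels of VIS410 to the placebo arm".

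Protocol 9.3.5 opens its symptom section with "The difference between VIS410 and placebo will be assessed as outlined below". What it then outlines is frequency tables and "Descriptive statistics of the duration of each of the subject-reported symptoms of influenza-like illness by treatment group".

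In SAP 9.1.1, time to resolution of the total, domain and component FluPRO scores "will be summarized using n, mean, SD, median, minimum, and maximum". In addition, "Kaplan-Meier methods will also be used to calculate the median time, 25th percentile, and 75th percentile time to resolution". On the level of presentation: "These summaries will be by treatment group and include the combined low-dose and high-dose VIS410 groups in the mITT population". The planned tables (14.2.1.2A/B, 14.2.1.5A/B and 14.2.1.6A/B) and figures (14.2.2.1 to 14.2.3.2) are summaries, Kaplan-Meier estimates and plots of the same quantities.

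SAP 9.1.1 uses two rules for when a score has resolved. Time to resolution is the latest time among the component items, each resolved at 0 or 1. Duration is primarily the earliest day from 2 consecutive means of 1.0 or less, with the item-based maximum as exploratory. For duration, subjects not resolved by Day 10 are summarized as 10 days.

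**The concern.** The plan asks a comparative question and then specifies no comparative quantity. Per-arm medians and quartiles without intervals invite readers to subtract one median from another. In a trial of about 50 per arm, they would have no stated uncertainty for the result.

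The second risk is selection. With no contrast named, the symptom effect that reaches the report could be picked once treatment codes are known. That matters because Protocol 1.4 presents the study as a step toward trials in hospitalized patients. Protocol 1.3 also already reports a 2-day shortening of upper respiratory symptoms in the challenge study, which readers will use as a yardstick.

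**Working it through.** **1. Treatment of comparable endpoints in the SAP**

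| Endpoint | Between-arm comparison | Interval |
|---|---|---|
| Viral load AUC, peak viral load (SAP 11.2) | t-test, or a transformed or non-parametric alternative | none named |
| Proportion virus-negative, Days 3, 5, 7 (SAP 11.2) | chi-square versus placebo | none named |
| Time to viral resolution (SAP 11.3) | none | 95% CI about each arm's median |
| Complications, adverse events (SAP 9.1.3, 12.1) | none | exact 95% CI on each arm's percentage |
| FluPRO time to resolution and duration (SAP 9.1.1) | none | none |

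The symptom time endpoint is the only row with neither. SAP 4.1 sets a general two-sided 0.05 convention for comparisons but assigns no comparison to this endpoint. The optional exploratory analyses in SAP 9.1.1 name no contrast either.

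**2. Choices left open**

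Scores: 1 total + 6 domains + 3 components = 10. Resolution rules: 2. Contrasts with placebo: low dose, high dose, pooled = 3. That gives 10 × 2 × 3 = 60 possible comparisons before choosing the effect measure.

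**3. Precision of the missing contrast**

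The plan has no figure to reproduce, because both documents say no sample size calculation was done. Inputs:

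- 150 subjects at 1:1:1 gives 150 / 3 = 50 per arm (SAP 2.2, 2.4).
- The mITT share is not given. Assumed 80% to 100%, so 40 to 50 per arm and 80 to 100 pooled.
- The SD of time to resolution, capped at 10 days, is not given. Assumed 2 to 4 days.

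Approximate 95% half-width = 1.96 × SD × √(1/n₁ + 1/n₀):

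- One dose, best case: 1.96 × 2 × √(1/50 + 1/50) = 0.78 days.
- One dose, worst case: 1.96 × 4 × √(1/40 + 1/40) = 1.75 days.
- Pooled, best case: 1.96 × 2 × √(1/100 + 1/50) = 0.68 days.
- Pooled, worst case: 1.96 × 4 × √(1/80 + 1/40) = 1.52 days.

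At the middle SD of 3 days with 50 per arm, the half-widths are 1.18 and 1.02 days. These figures assume a common SD and complete diaries to Day 10. Dropout would widen the intervals somewhat.

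**The case against.** The strongest reply is that the trial is openly descriptive on efficacy. Protocol 1.1 warns that the sample is too small to establish efficacy statistically, SAP 2.3 disclaims formal testing, and the primary objective is safety. This stands as a reason not to require a p-value. It does not explain leaving out an estimated difference with its interval, which is also descriptive. SAP 2.3 itself turns to 95% intervals for evaluating treatment differences in adverse events straight after disclaiming testing.

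Three stronger readings are tempting, and the documents do not support them.

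- A reader might infer that the planned output cannot answer the objective at all. That goes too far. Mean, SD and n are planned for each arm and for pooled VIS410, so an approximate unadjusted difference and interval can be worked out by hand. Because unresolved durations are set to 10 days, the planned mean duration is also close to a restricted mean through Day 10, apart from missing diaries and dropout. What is absent is the prespecified contrast.
- A reader might infer that the SAP breaks a promise in the protocol. Protocol 9.3.5 ties the difference to the outline that follows it, and that outline is descriptive. The SAP delivers it and adds Kaplan-Meier estimates. The mismatch between objective and analysis starts in the protocol and carries into the SAP.
- A reader might infer that symptoms alone lack a between-arm interval. The SAP's adverse event intervals are on per-arm percentages, and time to viral resolution has only a per-arm interval about the median. The nearest like-for-like shortfall is therefore that per-arm interval, while the between-arm tests apply to the viral load measures.

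The table shells are a separate document and could contain more. They cannot be checked here.

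**Conclusion.** The point holds as a gap in prespecification. The objective and Protocol 9.3 call for VIS410 to be compared with placebo on time to symptom alleviation, and no between-arm estimate or confidence interval is planned for any FluPRO time endpoint. Lack of power excuses a missing test but not a missing effect estimate.

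Under the assumed SD and mITT share, the interval would be roughly ±0.8 to ±1.8 days for one dose and ±0.7 to ±1.5 days for pooled VIS410. That is wide, but narrower than the 2-day figure from the challenge study, so it would still inform a reader. The comparison is only for scale, since that figure concerns upper respiratory symptoms after experimental infection.

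The gap does not invalidate the plan, and the data needed to close it are already collected. It is a cheap improvement.

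**What to change.** Add one analysis to SAP 9.1.1, before any unblinded output is produced, including the optional interim looks in SAP 13:

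- **Endpoint:** total symptom score, under the SAP's primary duration rule (2 consecutive means of 1.0 or less).
- **Population:** mITT.
- **Contrasts:** each dose versus placebo, and pooled VIS410 versus placebo.
- **Estimate:** difference in restricted mean time through Day 10 with a 95% CI, labelled descriptive and without a p-value.
- **Adjustment:** baseline total score may be included. It is optional, but the choice should be stated in advance.

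The other scores and the item-based rule can stay as planned, as supporting description. The cost is one extra table, with no new data and no extra subjects. The downside is that the interval will be wide, and the report will have to show that openly.

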3.2 Secondary Endpoints

- The incidence, severity, and duration of signs and symptoms of influenza-like illness as assessed by the FluPRO questionnaire after a single IV dose of VIS410
- Percentage of participants requiring hospitalization for influenza-related complications
- Duration of hospitalization for influenza-related complications
- Percentage of participants with complications of influenza
- Percentage of participants with influenza A relapse/reinfection
- VIS410 PK parameters (C_{max} , t_{max} , $AUC_{0-\infty}$, AUC_{0-last} , $t_{1/2}$, V_d , CL) in serum
- The difference between VIS410 and placebo treatment groups in viral AUC from nasopharyngeal swabs
- The difference between VIS410 and placebo treatment groups in peak viral load and time to resolution of viral load from nasopharyngeal swabs

- Titer of anti-VIS410 antibody-positive samples

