16.3 FluPRO Questionnaire

The FluPRO questionnaire collects information on influenza symptoms over the last 24 hours. These questions have possible answers of Not at all, A little bit, Somewhat, Quite a bit, or Very much. 'Not at all' is considered 'no symptom'.

1. Runny or dripping nose
2. Congested or stuffy nose
3. Sinus pressure
4. Scratchy or itchy throat
5. Sore or painful throat
6. Difficulty swallowing
7. Teary or watery eyes
8. Sore or painful eyes
9. Eyes sensitive to light
10. Trouble breathing
11. Chest congestion
12. Chest tightness
13. Dry or hacking cough
14. Wet or loose cough
15. Felt nauseous
16. Stomach ache
17. Felt dizzy
18. Head congestion
19. Headache
20. Lack of appetite
21. Sleeping more than usual
22. Body aches or pains
23. Weak or tired
24. Chills or shivering
25. Felt cold
26. Felt hot
27. Sweating

For numeric summaries, Not at all = 0; A little bit=1; Somewhat=2; Quite a bit=3; Very much=4.

These questions have possible answers of Never, Rarely, Sometimes, Often, Always. 'Never' is considered 'no symptom'.

28. Sneezing
29. Coughing
30. Coughed up mucus or phlegm

For numeric summaries, Never = 0; Rarely = 1; Sometimes =2; Often = 3; Always = 4'.

These questions have possible answers of 0 times, 1 time, 2 times, 3 times, 4 or more times. '0 times' is considered 'no symptom'.

31. How many times did you vomit?
32. How many times did you have diarrhea?

For numeric summaries 0 times = 0; 1 time = 1; 2 times = 2; 3 times = 3; 4 or more times = 4.

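### The FluPRO duration rule gives 0 days to a symptom that is absent at Baseline and present on Day 2, conflicts with the rest of its paragraph, and rests on two definitions of no symptom

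*SAP*

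**What the plan says.** The secondary endpoint (SAP 3.2) is "The incidence, severity, and duration of signs and symptoms of influenza-like illness as assessed by the FluPRO questionnaire". Protocol 9.3.5 asks for "Descriptive statistics of the duration of each of the subject-reported symptoms of influenza-like illness by treatment group".

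SAP 9.1.1 builds duration from the daily diary, Day 1 (Baseline) to Day 10:

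- **Item.** Duration is the first day of two consecutive no-symptom answers. No symptom covers the two lowest response options, that is, a score of 0 or 1.
- **Total, domain and component scores.** Duration is "primarily defined as the earliest visit day from 2 consecutive means" at or below 1.0, and also "as an exploratory endpoint as the maximum value of duration across the individual symptoms questions" that make up the score.
- **Zero rule.** For a subject without symptoms "at Baseline for a question, total symptom score, domain symptom scores, and component symptom scores, duration will be defined as zero for that question".
- **Day 10 rule.** A subject without two consecutive clear days by Day 10 is listed as >10 and summarised as 10.

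The same section says of time to resolution that "a value of 0 or 1 corresponds to resolution of that symptom". SAP 16.3, which reproduces the questionnaire and its numeric coding, says for questions 1 to 27 that "Not at all' is considered 'no symptom". It limits the other two question groups to their lowest option in the same way, so no symptom there is a score of 0 only. SAP 16.1, which lists changes to the protocol's analyses, does not mention the difference.

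**The concern.** The zero rule has no exception for a symptom that begins after Baseline. Baseline is the last value before dosing (SAP 4.1), so a symptom that starts after the infusion and is in the Day 2 diary can be reported as lasting 0 days. If it never clears by Day 10, the zero rule and the Day 10 rule both apply and give opposite answers.

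Two further gaps leave room for different programming of the same diary. No symptom has two definitions. The zero rule also names the total, domain and component scores in its condition, gives no baseline criterion for them, and ends by assigning zero to a question.

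Late onset need not be balanced between arms. Protocol 1.3 reports more gastrointestinal events on VIS410 than on placebo in VIS410-102. In earlier studies such events began during the infusion or within hours of it. FluPRO has a gastrointestinal domain and a 24-hour recall, so a Day 2 diary can record them.

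**Working it through.** The plan states no figure to reproduce. The check applies the rules to constructed diaries; none is trial data.

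**Inputs.** Diary days 1 to 10 and the duration rules come from SAP 9.1.1. Item scores 0 to 4 come from SAP 16.3. The threshold *t* is 1 for an item under 9.1.1, 0 under 16.3, and 1.0 for a mean score.

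**Rules.**
- Search rule: the smallest day *d* with the scores on *d* and *d*+1 both ≤ *t*; if none, >10.
- Zero rule: 0 if the Day 1 score is ≤ *t*, whatever follows.

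**1. Onset after Baseline (9.1.1 thresholds)**

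| Diary, Days 1 to 10 | With zero rule | Search rule alone |
|---|---|---|
| Item 0, then 4 on Days 2–10 | 0 | >10 |
| Item 0,3,3,3,3,0,0,0,0,0 | 0 | Day 6 |
| Item 0,3, then 0 | 0 | Day 3 |
| GI domain mean 0; 2.25 on Days 2–3; then 0 | 0, if the rule applies to scores | Day 4 |
| Item 0,0,4,4,4,4,4,1,1,1 | 0 | Day 1 |

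The GI mean on Days 2–3 takes nausea 2, stomach ache 2, vomiting 1 and diarrhea 4: (2+2+1+4)/4 = 9/4 = 2.25. All four items are 0 on Day 1, so this case meets either definition of no symptom.

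In the last row Days 1 and 2 are both clear, so the search rule stops at Day 1 before the symptom appears. The zero rule therefore makes a material difference only when the threshold is exceeded on Day 2 (complete diary). Later onset is missed by the search rule itself.

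**2. Two definitions of no symptom.** Item 1,3,3,3,2,2,1,1,0,0:
- 9.1.1 throughout: Day 1 score 1 ≤ 1, so 0.
- 16.3 at Baseline, 9.1.1 afterwards: first pair ≤ 1 is Days 7–8, so Day 7.
- 16.3 throughout: first pair of zeros is Days 9–10, so Day 9.

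**3. Exploratory maximum of item durations**
- X = 2,2, then 1 gives 3. Y = 0,4,4,4,4, then 1 gives 0 with the zero rule and 6 without. The maximum is max(3,0) = 3 against max(3,6) = 6.
- A = 3 on Days 1–6, then 1 gives 7. B = 0,4,4, then 1 gives 0 or 4. The maximum is 7 either way.

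So an item-level zero changes this endpoint only when the late-onset item would have lasted longest.

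**4. Mean-based scores.** One item at 4 adds 4/32 = 0.125 to the total score and 4/4 = 1.0 to the GI domain. A single new symptom seldom decides the total score; a small domain is more exposed.

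**The case against.** The strongest reply is that this concerns wording for a descriptive endpoint. There is no formal testing, p-values are informational only, and Protocol 1.1 says the sample does not support a determination of efficacy. The listed duration tables (14.2.1.6A and B) are at score level, and no table of item durations is listed. Time to resolution carries no zero rule. Symptom AUC, by-visit summaries and AE/AESI reporting are unaffected. All of this stands and limits the reach. It does not make the zero correct: item durations are called for in the protocol, and the zero rule's own condition names the scores.

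On the definition, 9.1.1 is the operative text. Its by-visit summaries and the table titles also use 0 or 1, and it points to the appendix only for the questions and numeric coding. So 16.3 is the outlier, and the Day 7 and Day 9 results need a reader to prefer the appendix. That stands; the remedy for this part is one correction to 16.3.

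Three stronger readings are tempting, and the documents do not support them:

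- *The zero rule accounts for all missed late onset, so deleting it is enough.* The diary 0,0,4,… gives Day 1 without it.
- *The zero rule is why an ill subject with a low mean score gets almost no duration.* A mean at or below 1.0 on Days 1 and 2 gives Day 1 without the rule. That follows from the prespecified 1.0 cut-off.
- *The gastrointestinal data show a bias of known size in favour of VIS410.* Earlier events mostly resolved within a day, and the loose-stool events with the diphenhydramine plus NSAID pretreatment in VIS410-102 were mild. Some would score 1 or less. Others would not: Grade 1 diarrhea in Protocol Appendix 2 includes 3 to 4 loose stools a day, which item 32 would score 3 or 4 if reported as diarrhea ("3 times = 3; 4 or more times = 4"). Earlier event rates cannot be converted into a number of wrong zeros.

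**Conclusion.** The point holds in limited form. As written, the plan gives 0 days to a symptom that first exceeds the threshold on Day 2, conflicts with the Day 10 rule when that symptom persists, uses two definitions of no symptom, and states no baseline criterion for scores. These produce wrong or conflicting values for a named secondary endpoint, so this is more than missing detail.

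For an affected subject the difference runs from 0 against Day 3 for a one-day episode to 0 against >10. The overall size is unknown, because the documents give no baseline FluPRO distribution and no rate of Day 2 onset by item. The direction between arms is plausible for gastrointestinal items but not established. The primary safety objective is not touched. The conclusion rests on a literal reading of 9.1.1, on complete diaries and, for the score example, on the zero rule applying to scores. It should be settled before unblinding, so that the choice of reading cannot depend on results.

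**What to change.** Before unblinding:

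- **(a)** Correct SAP 16.3 so that no symptom is a score of 0 or 1 for all three question groups, matching 9.1.1.
- **(b)** Replace the zero rule. Summarise each item duration and each mean-based score duration in mITT subjects above the threshold at Baseline (item score > 1; score mean > 1.0), and report per arm how many were not above it. SAP 9.1.2 already restricts time to normal temperature in this way, to mITT subjects with a raised baseline temperature.
- **(c)** Tabulate by arm, in all mITT subjects, the symptoms that first exceed the threshold after Baseline. This also captures onset after two clear days. Give their duration descriptively only, because that subset is defined by a post-randomisation event.

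Keep the prespecified exploratory maximum of item durations, using the item durations from (b). Late-onset items then leave that maximum and appear in (c).

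The cost is SAP wording and derivation code. Some duration tables will have fewer subjects, and the subset will differ from score to score. The table shells are to be completed only after the SAP text is final (SAP 16.7).
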